6.6 Safety Analysis

[figure not shown]
Collection of AEs in the study eCRF will be limited to AEs leading to study treatment discontinuation or dose modification, or trial withdrawal. All SAEs will be reported by the investigator via a dedicated SAE report form directly to Boehringer Ingelheim Global Pharmacovigilance as described in [section 7.2](#). As hospitalization SAEs are reflected in claims records, a patient-level review comparing hospitalization claims entries with reported SAEs for each respective patient will take place after completion of the 12-month visit in order to identify any hospitalizations of which the investigator was potentially unaware. The investigator will receive information of any SAE identified through this process and report it using the standard SAE reporting process (See [section 7.2](#)).

SAE data for analysis will be drawn from the Boehringer Ingelheim Safety Database.

Analysis of non-serious AEs (leading to study treatment discontinuation or dose modification, or trial withdrawal) will be performed on the study database, as these are entered in the eCRF only.

Safety analyses will be descriptive in nature. No hypothesis testing is planned prospectively.

AEs will be coded using the current version of the Medical Dictionary for Regulatory Activities (MedDRA) coding dictionary at the time of reporting, and recoded to the MedDRA version current at the time of database integration. Summary tables and listings will be produced to compare the incidence of AEs across treatment groups, by Preferred Term (PT)/System Organ Class (SOC) and also by medical concept (MedDRA Standardized Medical Queries (SMQ) or custom Boehringer Ingelheim searches termed Pharmacovigilance (PV) endpoints). All AEs with an onset after the first dose of trial medication and up to 21 days after the last dose of trial medication will be assigned to the on-treatment period. Other AEs will be assigned either to the screening period, post-treatment period or the post-study period as appropriate.

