#### **On-Study** Treatment

Triple therapy is defined as any of the combination of ICS, LABA and LAMA drugs that a patient's physician chooses. Therefore, the following combination of COPD medications categories will count as triple therapy on study, differentiating between free combination and FDC:

- Triple Therapy Free Combinations
  - $\circ$  ICS + LABA + LAMA
  - ICS-LABA + LAMA
  - ICS + LAMA-LABA
- Triple Therapy FDC
  - o LAMA-LABA-ICS

Patients may switch or discontinue study treatment over the 12 month observation period.

For the purpose of analysis, patients will be classified as Continued Original Randomized Treatment, Continued In-Class Randomized Treatment, or Off Randomized Treatment as described below. The categories are non-overlapping. Changes in targeted COPD concomitant medications do not apply to this classification.

- **Continued Original Randomized Treatment**: Patients taking the same COPD medication as originally initiated for randomized COPD study treatment.
  - Stiolto Respimat patients taking Stiolto Respimat.
  - Triple Therapy patients taking the same individual components of ICS plus LAMA plus LABA as initiated at Baseline.
- Continued In-Class Randomized Treatment: This definition only applies to Triple Therapy patients who made changes to the triple therapy components originally initiated for their randomized COPD study treatment (i.e., those not considered "Continued Original Randomized Treatment").
  - Triple Therapy patients taking any combination of ICS plus LABA plus LAMA that meets the study definition of triple therapy will be considered "Continued In-Class Randomized Treatment" if changed from original study medications.

•

- **On Treatment**: Patient is categorized as Continued Original Randomized Treatment or Continued In-Class Randomized Treatment (the duration of time is from randomization until the patient is no longer in one of these two categories)
  - Patients who have a temporary treatment interruption of  $\leq 28$  days will still be considered On Treatment provided they resume treatment that meets the On Treatment definition within 28 days of when the treatment was first interrupted.
    - If the On Treatment study medication is resumed with a new start date ≤ 28 days of the stop date, it will be classified as a temporary treatment interruption.

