    - If the On Treatment study medication is resumed with a new start of >28 days of the stop date, or if the On Treatment study medication is not resumed before EOS or last contact, it will be classified as a treatment discontinuation.
    - For Triple Therapy patients, a >28 day continuous window in which they are not receiving all 3 components of triple therapy will be considered treatment discontinuation. This could occur due to a >28 treatment interruption of a single component, or overlapping treatment interruptions of more than one component such that the patient does not receive triple therapy for a continuous window of >28 days.
- **Off Randomized Treatment**: Patient is categorized as Off Treatment (the duration of time is from when the patient is no longer On Treatment until EOS or last contact)

On Treatment will also be used for the safety analysis (Section 6.3).

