#### 5.1.2 Per Protocol (PP) Population

No per-protocol set is defined and no analysis is planned.

Version 3.0 March 2021

CONFIDENTIAL

The Safety population includes all randomized patients who received a prescription of any study treatment (Stiolto Respimat or triple therapy).

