#### 6.3 Reporting and Analysis Periods

AEs and SAEs will be reported from the time a patient signs consent until the EOS visit at 12 months or until the patient discontinues the trial. However, only "on treatment" AEs and SAEs will be included in analysis. "On treatment" medications for each treatment arm are defined in section 4.4.2. For the safety analysis time period, all AEs will be considered "on treatment" (see section 4.4.2) if the AE start date is within 21 days after the On Treatment study medication end date or until EOS, whichever comes first.

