# 7.0 IMPORTANT PROTOCOL VIOLATIONS (IPVs)

IPVs will be reported in a listing. Potential IPVs include:

- Inclusion or Exclusion criteria not met.
- Informed Consent not documented prior to study randomization.
- Initial prescription provided for randomized study treatment was incorrect. (This does not include changes to study medication subsequent to initiation of study treatment.)

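### The SAP opens the on-treatment AE window at randomization and Protocol 6.6 opens it after the first dose; the change is not declared, and wrong-regimen and never-started patients are not handled consistently

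*SAP*

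**What the plan says.** **Start of the window.** Protocol 6.6 assigns to the on-treatment period "All AEs with an onset after the first dose of trial medication and up to 21 days after the last dose of trial medication" and places all other AEs in a screening, post-treatment or post-study period. SAP 4.4.2 (On-Study Treatment) defines On Treatment differently: "the duration of time is from randomization until the patient is no longer in one of these two categories". The closing line of that section applies the definition to safety.

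**What is analysed.** SAP 6.3 states that only on-treatment "AEs and SAEs will be included in analysis". It treats an AE as on-treatment "if the AE start date is within 21 days after the On Treatment study medication end date or until EOS, whichever comes first". That is an upper limit; no lower limit tied to first dose is given. SAP 2.1, which lists the changes to the planned analysis (including the dropped medical-concept AE tables), does not mention the window.

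**Denominator.** SAP 5.1: "The Safety population includes all randomized patients who received a prescription of any study treatment" (Stiolto Respimat or triple therapy). Protocol 6.2.2 defines the same set, and SAP 6.4 reports all AE analyses on it.

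**Who is On Treatment.** The main category in SAP 4.4.2 is "Patients taking the same COPD medication as originally initiated for randomized COPD study treatment", narrowed for the Stiolto arm to patients taking Stiolto Respimat. The in-class category is open to triple-therapy patients only. SAP 7.0 foresees a protocol violation of the form "Initial prescription provided for randomized study treatment was incorrect".

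**The concern.** Protocol 4.1 gives patients a prescription, not drug. The first dose may follow randomization by days or weeks, or may never be taken. The choice between randomization and first dose as the start of the window therefore has consequences in this design.

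Two separate things go wrong. First, an admission after randomization but before the first dose is excluded from the on-treatment tables under the protocol and included under the SAP, so it is attributed to drugs not yet taken. Second, entry to the denominator needs only a prescription, while entry to the numerator needs the randomized regimen to be taken. Some patients can then sit in the denominator without being able to contribute an event. Because SAP 6.3 applies its restriction to every AE and SAE analysis, the SAE and fatal-AE tables are included.

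**Working it through.** The plan gives no AE rate, no share of patients who never start, and no time from randomization to first dose, so there is no figure of its own to reproduce. The check compares the definitions and then illustrates scale under stated assumptions.

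**1. Definitions by type of patient** (reading treatment group in the safety tables as the randomized arm, as the category names in SAP 4.4.2 suggest)

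| Patient | Protocol 6.6 and 6.2.2 | SAP 4.4.2, 5.1 and 6.3 |
|---|---|---|
| Starts the assigned regimen late, SAE before first dose | In denominator; SAE not on-treatment | In denominator; SAE on-treatment |
| Randomized to Stiolto, prescribed and started on triple therapy | In denominator; AEs after first dose of trial medication are on-treatment | In denominator; fits neither On Treatment category, so AEs are not analysed |
| Prescribed, never starts | In denominator; no first dose, so no on-treatment AE | In denominator; classification not stated |

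In the second row, no On Treatment medication end date exists from which the 21-day tail could run. A triple-randomized patient started on Stiolto falls out in the same way.

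The third row has two readings. If On Treatment requires taking the drug, the patient's AEs are not counted and the arm's percentage is diluted. If On Treatment simply runs from randomization, the AEs are charged to the arm and there is no such dilution. For the same patient these are alternatives, not cumulative harms.

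**2. Which AEs can fall before the first dose.** Protocol 7.1 limits non-serious AEs to those leading to treatment discontinuation, dose modification or trial withdrawal. Before a first dose, that leaves essentially SAEs and AEs leading to withdrawal.

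**3. Illustration of pre-dose events.** Assumed: 12-month risk r, constant hazard h = −ln(1−r)/365, and a gap of g days for every patient. The addition to the reported percentage is r − [1 − exp(−h(365−g))].

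For r = 10% and g = 14: h = 0.10536/365 = 0.0002887; 1 − exp(−0.0002887 × 351) = 9.636%; the addition is 10 − 9.636 = 0.364 percentage points. Arm size is 703/2 = 351.5 (SAP 4.2, 1:1 allocation), so patients with a pre-dose event number 351.5 × [1 − exp(−0.0002887 × 14)] = 1.42 per arm.

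| r | g = 3 | g = 7 | g = 14 | g = 28 |
|---|---|---|---|---|
| 5% | 0.040 | 0.093 | 0.187 | 0.375 |
| 10% | 0.078 | 0.182 | 0.364 | 0.730 |
| 20% | 0.147 | 0.343 | 0.688 | 1.381 |

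(percentage points added)

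**4. Illustration of dilution.** Assumed: a share f of the arm is prescribed but never starts the randomized regimen, and its AEs are not counted. Reported percentage = r(1−f). With r = 10%, f = 2, 5, 10 and 20% gives 9.8, 9.5, 9.0 and 8.0%. Equal f in both arms leaves the ratio of percentages unchanged. With f = 5% in Stiolto and 15% in triple therapy, the Stiolto/triple ratio is multiplied by 0.95/0.85 = 1.12; with the shares reversed, by 0.85/0.95 = 0.89.

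The effects in steps 3 and 4 have opposite signs.

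**The case against.** The strongest reply is that randomization is a deliberate proxy for treatment start. Study treatment is recorded at the baseline visit, where randomization also occurs, and SAP 4.4.2 speaks of triple components as begun at Baseline. The SAP does not say whether a recorded start date means first intake or the date of prescribing, so a first-dose rule may be less exact than it looks. Safety is descriptive, without tests. The primary and secondary effectiveness analyses are ITT and do not use this window, and wrong initial prescriptions are already listed as protocol violations.

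All of this limits the consequence and stands to that extent. It does not remove the conflict: a proxy adopted in place of the protocol's rule should be declared, and a violations listing does not return those patients' AEs to the tables.

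A reader might infer three stronger things that the documents do not support:

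- **That the SAP departed from the protocol on the denominator.** Protocol 6.2.2 uses the same prescription-based set. Its mismatch with the numerator is a weakness, but not an undeclared change, and restoring a first-dose window would not remove it.
- **That AE percentages are biased low.** Pre-dose events raise them and dilution lowers them. The net sign is unknown.
- **That triple therapy suffers more because it needs more prescriptions filled.** Eligible patients already take a LAMA, a LABA or an ICS/LABA. One added product can complete triple therapy for the LAMA or ICS/LABA users, and SAP 4.4.2 also allows a single fixed-dose triple. The direction between arms cannot be derived.

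**Conclusion.** The point holds as a conflict between protocol and SAP that reaches every AE table and is absent from SAP 2.1. Following the SAP as written counts pre-dose SAEs and withdrawal AEs as on-treatment. It also removes the AEs of patients started on the wrong study regimen while keeping those patients in the denominator, and it leaves never-starters unclassified in the public text. An empty bullet beside the On Treatment definition may hide a withheld category, so the last part is limited to what can be read.

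The effect is probably small. The pre-dose part is under 0.75 percentage points at an assumed 10% risk for gaps up to 28 days, and about 1.4 percentage points at 20% risk and 28 days. These figures assume a constant hazard and the same gap for everyone. Patients enter because they are judged not controlled, so an early hazard above the average would make the pre-dose part larger. Dilution is proportional to a never-started share that the documents do not give. Only descriptive safety tables are touched. The correction is worth making because it is cheap and the tables concern SAEs and deaths.

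**What to change.** 1. In SAP 6.3, give safety its own window, starting at the first recorded study-medication start date in line with Protocol 6.6, and assign earlier AEs to a pre-treatment period. Alternatively, declare and justify randomization as the start in SAP 2.1.
2. State which start date applies when a triple component continues from pre-study therapy. A rule that waits until all three classes are in use is not the Protocol 6.6 rule and would drop AEs in the triple arm only.
3. State how never-starters and wrong-regimen patients are classified, and report their numbers by arm, unless the withheld part of SAP 5.2 already does so.
4. Keep the protocol's prescription-based safety set, and add AE and SAE tables restricted to patients with a recorded start, by regimen actually taken.
5. In the same edit, settle the end of the window: SAP 6.3 cuts the 21-day tail at EOS and Protocol 6.6 does not.

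The cost is SAP wording, programming and a few extra tables. SAP 4.4.2 already relies on medication start and stop dates. The downside is that start dates are site-reported and may record prescribing rather than first intake; a footnote should say which.

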While the benefits of ICS therapy are well documented across a broad spectrum of patients with asthma, their benefits in the COPD population appear to be more targeted to select patient phenotypes. Specifically, the benefit appears to be most robust in patients with severe COPD with a history of frequent exacerbations or with an inflammatory/allergic component to their disease. In addition, ICS therapy is associated with localized symptoms such as voice hoarseness and thrush, as well as systemic diseases such as upper respiratory tract infections and osteoporosis.

The Withdrawal of Inhaled Steroids during Optimized Bronchodilator Management (WISDOM)⁸ trial explored the impact of withdrawing ICS in patients concurrently receiving LAMA/LABA combination therapy. In this randomized, double-blind, non-inferiority designed study the risk of moderate or severe exacerbations was similar between those who had their ICS withdrawn versus those who continued. A logical follow-up research question from the WISDOM study is to assess patients who are not controlled on their current therapy of ICS-LABA, LABA alone or LAMA alone, to see if change in therapy to LAMA/LABA FDC therapy is similar in effect to triple therapy. Studying the question in a manner that assesses patients as therapy is “stepped-up” is reflective of usual clinical practice and would provide valuable and relevant real-world evidence to both practicing clinicians and health care payers. In addition, the GOLD 2017 update specifically states that “more evidence is needed to draw conclusions on the benefits of triple therapy LABA/LAMA/ICS compared to LABA/LAMA.” To this end, the proposed study, AIRWISE: Assessment In a Real World setting of the effect of Inhaled Steroid-based triple

⁸ Magnussen H, Disse B, Rodriguez-Roisin R, et al. Withdrawal of Inhaled Glucocorticoids and Exacerbations of COPD. N Engl J Med. 2014;317:1285-94.

therapy versus the combination of tiotropium and olodaterol on reducing COPD Exacerbations, is a non-inferiority trial of community-based COPD patients randomized to either Stiolto Respimat or triple therapy following a physician decision to escalate therapy. The decision to escalate therapy will be at the discretion of the treating physician. Patients will be treated according to routine clinical practice and followed for clinical (exacerbations, etc.) [REDACTED]

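### The SAP leaves out of the safety tables events that start more than 21 days after one triple-therapy component lapses, even if the ICS continues; this is undeclared and not reconciled with Protocol 6.6

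*SAP*

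**What the plan says.** SAP 4.4.2 (On-Study Treatment) sets the rule for triple-therapy patients: "a >28 day continuous window in which they are not receiving all 3 components of triple therapy will be considered treatment discontinuation". One missing product is enough: "This could occur due to a >28 treatment interruption of a single component". No exception is made when the ICS continues. The resulting off-treatment state is not reversed by a later restart, because "the duration of time is from when the patient is no longer On Treatment until EOS or last contact". The same section carries the On Treatment status into the safety analysis.

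SAP 6.3 analyses only AEs and SAEs classed as on treatment. An event qualifies if it starts "within 21 days after the On Treatment study medication end date or until EOS, whichever comes first".

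Protocol 6.6 defines the period differently. Events after the first dose and "up to 21 days after the last dose of trial medication will be assigned to the on-treatment period". Events outside it go to a screening, post-treatment or post-study period; nothing says that they are left out of the analysis.

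SAP 2.1 lists the changes to the planned analysis. One of them concerns safety (the SMQ and custom searches are dropped), but the narrower safety window is not mentioned.

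**The concern.** SAP 4.4.2 allows triple therapy as free combinations, for example ICS-LABA plus a LAMA. A patient who stops the LAMA and stays on the assigned ICS-LABA for the rest of the year is off treatment for safety, and events after the 21-day tail do not reach the tables. This is a realistic course: ICS/LABA is a qualifying pre-study therapy, so dropping the added LAMA simply returns such a patient to the earlier class of treatment.

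The added ICS is the contrast that the trial studies, and ICS harms are part of its rationale: Protocol 1.1 states that "ICS therapy is associated with localized symptoms such as voice hoarseness and thrush, as well as systemic diseases". SAP 6.4.1 reports the number and percentage of patients with AEs in the safety population and states no adjustment for exposure. When a patient's event window shrinks, the denominator does not, so each such cut can only lower that arm's percentages. SAEs and fatal AEs are affected in the same way as milder events.

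**Working it through.** **No figure to reproduce.** The plan gives no number for this point. The check is a comparison of texts followed by day counts.

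**1. The passages side by side**

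| Situation | SAP 4.4.2 and 6.3 | Protocol 6.6 |
|---|---|---|
| Triple patient stops one non-ICS product for more than 28 days, ICS continues | Discontinued; events count to end date + 21 days | Counts to last dose of trial medication + 21 days; the term is not defined for several products |
| Stiolto or triple patient restarts after a gap of more than 28 days | Discontinued; events after the restart are lost once the tail has passed | Later doses of the same product move the last dose, so they count |
| Triple patient changes to another ICS plus LABA plus LAMA combination | Remains On Treatment | Not addressed |
| Stiolto patient changes to another LAMA plus LABA | Off treatment | Last Stiolto dose already taken, so the texts agree |
| Events outside the window | Not analysed | Assigned to another period |

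Stiolto is a single fixed-dose product, so the first row can arise only in the triple arm. A patient on the fixed-dose triple can reach it only by changing product.

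On whether a patient left on ICS-LABA is still taking trial medication: the SAP's end-of-study categories for study COPD medication include ICS + LABA, separate from taking none. That favours counting the remaining components, but does not settle the protocol's term.

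**2. One patient.** Assume a 365-day year and the ICS taken to day 365. Last counted day = min(stop day + 21, 365).

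| LAMA stop day | Last counted day | Uncounted days on ICS |
|---|---|---|
| 30 | 51 | 314 |
| 90 | 111 | 254 (254/365 = 70%) |
| 180 | 201 | 164 |
| 270 | 291 | 74 |

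**3. Average.** With the stop day T uniform over the year, the mean uncounted time is E[max(0, 344 − T)] = 344²/(2 × 365) = 162 days, or 44% of the year. The SAP does not say whether the end date is the component's stop date or the end of the 28-day window. On the later reading the mean is (365 − 49)²/730 = 137 days, or 37%.

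**4. Arm level.** Let f be the share of triple patients who drop a non-ICS component and keep the ICS to month 12. The documents do not give f; 10% to 30% is assumed.

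- Uncounted share of the arm's follow-up: f × 44.4% = 4.4% at f = 10% and 13.3% at f = 30%.
- On the later end date: f × 37.5% = 3.7% to 11.2%.
- With about 703 patients randomized 1:1 (about 351 per arm), f = 10% is about 35 patients and 15.6 person-years; f = 30% is about 105 patients and 46.7 person-years.

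**5. Reported percentage.** Assume a constant hazard and a true 12-month risk r. For affected patients, average 1 − exp(−h × min(s + 21, 365)/365) over stop days s = 1 to 365, with h = −ln(1 − r).

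- r = 20%: h = 0.223 and the average is 11.5%. Reported risk = (1 − f) × 20% + f × 11.5%, which is 19.2% at f = 10%, 18.3% at 20% and 17.5% at 30%.
- r = 10%: the reported risk is 9.6%, 9.1% and 8.7%.

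**The case against.** A reader might infer that only the triple arm is affected. The documents do not support that. The rule that a restart after more than 28 days is a discontinuation applies to both arms, so a Stiolto patient who resumes after a long gap also loses on-drug events.

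A reader might also infer that triple-arm harm is understated overall and the comparison tilted against Stiolto. That is not shown either. The single-component rule shortens the triple window, but in-class switching lengthens it, and only for triple patients. Which effect is larger cannot be determined from the documents.

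A third tempting reading is that the SAP plainly contradicts the protocol because the last dose has not been taken. Protocol 6.2.2 names the study treatments as Stiolto Respimat or triple therapy, so one can argue that a patient left on ICS-LABA has taken the last dose of triple therapy. The term needs defining. What stands without that argument is the treatment of restarts, and the exclusion of events that the protocol merely allocates to other periods.

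The size can fairly be called modest. The range needs every affected patient to drop a non-ICS component and keep the ICS to month 12; patients who drop the ICS itself lose no ICS time beyond the tail. A shift from 20% to 19.2% is small beside a standard error of √(0.2 × 0.8/351) = 2.1 percentage points. Non-serious hoarseness or thrush is recorded only if it leads to discontinuation, dose modification or withdrawal, so much of it would be missed under any window. Safety is descriptive, without testing. SAP 6.4.1 also promises a listing of all SAEs, which might be meant to be unrestricted, although SAP 6.3 makes no exception for it.

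These points limit the size and the direction. They do not remove the undeclared exclusion of collected events, including SAEs and deaths.

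**Conclusion.** The concern holds in this form. SAP 4.4.2 and 6.3 together remove from the safety tables every AE or SAE that starts more than 21 days after the On Treatment end date, and a triple patient reaches that date through a gap of more than 28 days in one component even while the assigned ICS continues. Protocol 6.6 does not provide for this exclusion, and SAP 2.1 does not declare it. The single-component route is specific to the triple arm; the restart rule is not; the net direction is uncertain.

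The 4% to 13% of follow-up, and the fall from 20% to between 19.2% and 17.5%, are upper-end illustrations. They rest on the assumed 10% to 30%, uniform stop times, a constant hazard, and an end date equal to the component's stop date. Because only about 703 patients were enrolled and AE collection is already selective, a few lost serious events could still matter to a reader of the tables. The ITT primary analysis does not use this window and is unaffected. The change should be made, but the trial's main result does not depend on it.

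**What to change.** - In SAP 6.3, reconcile the safety window with Protocol 6.6 by one rule for both arms: it ends 21 days after the last recorded dose of any component of the randomized regimen, including in-class replacements and restarts. State for each arm which replacements count; the SAP's end-of-study step-over category already defines in-class changes for both.
- Add a summary of all AEs and SAEs from first dose to EOS by randomized arm, so that no collected SAE or death is left out whichever window is used.
- State whether the listing of all SAEs is restricted to on-treatment events.
- Declare the change in SAP 2.1.
- Keep the all-three-components rule for regimen persistence and for the on-treatment effectiveness sensitivity analysis.

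The cost is a few sentences and one extra set of tables. Patients are followed for 12 months regardless of treatment changes (Protocol 5.4), so the events are already collected, and component stop dates are already needed for the present rule. The downside is that the triple window will include time on part of the regimen, some of it without an ICS and so close in drug class to the comparator. Events after the ICS was stopped should be flagged or footnoted.

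### As most naturally read, the SAP leaves adverse events on study drug restarted after a gap of more than 28 days out of the AE and SAE incidence summaries, which departs from Protocol 6.6 without being declared

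*SAP*

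**What the plan says.** SAP 4.4.2 (On-Study Treatment) defines On Treatment as one span: "the duration of time is from randomization until the patient is no longer in one of these two categories". The two categories are continuing the original randomized treatment and, for triple therapy only, continuing in class. Gaps are then sorted by length.

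- Resumed within 28 days: "it will be classified as a temporary treatment interruption", and the patient stays On Treatment.
- Resumed later: the SAP addresses this case directly ("If the On Treatment study medication is resumed with a new start of >28 days of the stop date") and calls it a discontinuation, in the same sentence as a drug that is never resumed.
- Triple therapy: "a >28 day continuous window in which they are not receiving all 3 components of triple therapy will be considered treatment discontinuation". A lapse in a single component is enough.

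From that point the patient is Off Randomized Treatment: "the duration of time is from when the patient is no longer On Treatment until EOS or last contact". No sentence brings a restarted patient back to On Treatment. The section ends by applying this status to safety as well.

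SAP 6.3 then says that only on-treatment "AEs and SAEs will be included in analysis". An event qualifies if it starts no later than 21 days after the end date of the On Treatment study medication, or by EOS if that is earlier.

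Protocol 6.6 draws the on-treatment period differently: "All AEs with an onset after the first dose of trial medication and up to 21 days after the last dose of trial medication". It has no gap rule. It allocates other events to other periods and does not say that they are left out of the analysis.

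**The concern.** A patient who lapses for five weeks and then takes the randomized drug for the rest of the year is labelled off treatment while taking it. An SAE in those months would be left out of the incidence summaries, although it occurred under exposure and the protocol calls it on-treatment. The same would apply to a fatal event, or to an AE that makes the patient stop a second time.

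The situation is plausible here. Patients fill their own prescriptions, only the baseline and 12-month visits are required, and Protocol 5.4 keeps patients under follow-up for the full 12 months whatever happens to treatment. Events after a restart will therefore be in the data. SAP 2.1 lists the changes to the planned analysis, including the dropped SMQ and custom-search outputs, but not this narrower window.

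**Working it through.** The plan states no figure on this point, so there is none to reproduce. The check is a count of days under each rule.

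**Inputs.** Gap limit 28 days (SAP 4.4.2). Extension 21 days (SAP 6.3 and Protocol 6.6). About 703 patients (SAP 4.2). Assumptions: EOS on day 365, and the restarted drug is taken until then.

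**Step 1: can any event on the restarted drug qualify?** Let S be the stop day and R the restart day. Under the SAP, if R − S > 28, the window closes on day S + 21. The earliest such restart is day S + 29. Since 29 − 21 = 8, the restart comes at least 8 days after the window has closed, so none can qualify, whatever S is.

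**Step 2: days on restarted drug that count.** Days from R to 365 number 365 − R + 1.

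| Stop day | Gap | Restart day | Days on restarted drug | Counted, SAP | Counted, Protocol 6.6 |
|---|---|---|---|---|---|
| 30 | 28 | 58 | 308 | 308 | 308 |
| 30 | 29 | 59 | 307 | 0 | 307 |
| 30 | 45 | 75 | 291 | 0 | 291 |
| 180 | 28 | 208 | 158 | 158 | 158 |
| 180 | 29 | 209 | 157 | 0 | 157 |
| 300 | 45 | 345 | 21 | 0 | 21 |

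One extra day of gap moves the count from all to none.

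**Step 3: one patient in full (assumed dates).** Stop on day 60, restart on day 95. The SAP window closes on day 60 + 21 = 81. Events on days 82 to 365 are excluded, including all 365 − 95 + 1 = 271 days on restarted drug. Protocol 6.6 excludes none of them; it also counts the off-drug days 82 to 94, because they precede the last dose.

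**Step 4: effect on the tables.** SAP 6.4.1 counts patients with AEs, not events, in the safety population. Looking only at where the window ends, the SAP numerator for any row is at most the protocol numerator, and the denominator is the same. Incidence is understated or unchanged. A patient already counted in a row before the gap is not lost from it.

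**Step 5: number of patients.** The documents give no restart frequency. Assuming 1% to 10%: 703 × 0.01 = 7.0 and 703 × 0.10 = 70.3.

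**Step 6: consistency within the SAP.** The EOS medication summary in SAP 4.4.2 reports a Stiolto patient who is taking Stiolto at EOS as on original randomized treatment. The same patient, after a long gap and a restart, is Off Randomized Treatment until EOS under the on-study classification.

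**The case against.** The strongest reply is textual. SAP 6.3 never mentions Off Randomized Treatment; it works from the end date of the On Treatment study medication. SAP 4.4.2 uses that same term for a drug resumed after a long gap. The end date could then be the final stop date, which gives the protocol's rule. This reading is possible. It conflicts, however, with On Treatment being a single span from randomization and with the Off period running to EOS. Even if it was intended, the text needs to say so.

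Three stronger conclusions are tempting, and the documents do not support them.

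- A reader might infer that the events vanish from every safety output. SAP 6.4.1 has a table of all collected AEs and a listing of all SAEs, and these titles suggest no period limit. SAP 6.3 states its restriction generally and makes no exception for them, so the ambiguity remains; an SAE listing would not restore the incidence tables in any case.
- A reader might infer that the data are lost. They are not. Under Protocol 7.2.1 SAEs are reported until the 12-month visit or trial discontinuation, whatever the treatment status. Only the summaries are in question.
- A reader might take the excluded share of on-drug days as the size of the problem. For the patient in Step 3 it is 271 / (60 + 271) = 82%. That is not a share of missing incidence, because the tables count patients and the dates are assumed.

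Nor can a direction of bias between arms be claimed. A lapse in one component triggers the rule for triple therapy, but in-class switching keeps only triple therapy patients On Treatment. The documents give no restart frequency by arm.

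It is also true that the safety analyses are descriptive and test no hypothesis. That limits the consequence but does not justify labelling exposed time as unexposed.

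**Conclusion.** The point holds for the AE and SAE incidence summaries, on the most natural reading of SAP 4.4.2 together with 6.3. For a patient who restarts after more than 28 days, no event on the restarted drug can enter the on-treatment window. Given the two day limits, that follows for any stop date. It is an undeclared departure from Protocol 6.6.

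The overall size is unknown. The range of about 7 to 70 patients rests entirely on the assumed 1% to 10%, and not each of them would have an event that changes a table. ITT effectiveness results do not depend on this rule. The point merits correction because the safety tables are meant to describe events under treatment, and the correction is cheap.

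**What to change.** For safety only, state in SAP 6.3 that the on-treatment period follows Protocol 6.6: from first dose to 21 days after the last recorded dose of the randomized treatment, capped at EOS. For triple therapy, the last dose is the last date on a regimen that meets the triple therapy definition. A restart after more than 28 days then counts as on-treatment. State also whether the all-collected-AEs table and the SAE listing in SAP 6.4.1 are limited to this period. The 28-day first-discontinuation rule can stay for effectiveness sensitivity analyses and treatment-change summaries.

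The cost is a sentence or two and a small programming change; the start and stop dates are already needed for the 28-day rule. There is a small downside: off-drug days before a restart count as on-treatment, as the protocol already specifies.

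An alternative is to count each interval of use plus 21 days, but that would be a third rule. In Step 3 it would leave out days 82 to 94, which Protocol 6.6 counts. It would also drop up to 28 − 21 = 7 days from gaps of 22 to 28 days that the SAP now keeps. If the sponsor prefers this or any other window, it should be declared in SAP 2.1 with its reason.
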